1.2 Rationale

The purpose of this study is to demonstrate the clinical efficacy of Seqirus' adjuvanted inactivated quadrivalent vaccine in adults 65 years of age and older. This randomized, observer-blind, non-influenza comparator-controlled study is intended to demonstrate that aQIV prevents RT-PCR confirmed influenza. This study is intended to fulfil a requirement of the accelerated approval pathway in the US. In particular to demonstrate the clinical benefit of aQIV, the quadrivalent version of Fluad, which was recently licensed for use in the US in adults 65 years and older.

2. OBJECTIVES

2.1 Primary Objective(s)

The primary and secondary efficacy objectives will be measured in all subjects in relation to cases of influenza occurring from 21 through 180 days after vaccination or through the end of influenza season, whichever is longer. In all cases, efficacy will be determined based on influenza cases caused by A (H1N1 and H3N2) and either B lineage.

Primary Efficacy Objective:

1. To demonstrate absolute vaccine efficacy of aQIV versus non-influenza comparator (Boostrix[®]) when administered as a single dose to prevent first occurrence RT-PCR-confirmed influenza, due to any strain of influenza regardless of antigenic match to the strains selected for the seasonal vaccine, in subjects \geq 65 years of age.

Primary Safety Objectives:

2. To evaluate the safety of aQIV through assessment for local and systemic solicited adverse events through Day 7 in a subset of subjects.
3. To evaluate the rates in each vaccine group of medically-attended adverse events within 30 days after the first occurrence RT-PCR confirmed ILI.
4. To evaluate the rates in each vaccine group of unsolicited adverse events for 21 days after vaccination and adverse events leading to withdrawal, serious adverse events (SAEs), adverse events of special interest (AESI), and new onset of chronic diseases (NOCD) for 365 days after vaccination.

2.2 Secondary Objective(s)

Key Secondary Efficacy Objective:

1. To demonstrate absolute vaccine efficacy of aQIV versus non-influenza comparator when administered as a single dose to prevent first occurrence culture-confirmed influenza, due to strains antigenically matched to the strains selected for the seasonal vaccine.

Secondary Efficacy Objectives:

2. To evaluate absolute vaccine efficacy of aQIV versus non-influenza comparator when administered as a single dose to prevent first occurrence culture-confirmed influenza, due to any strain of influenza regardless of antigenic match to the strains selected for the seasonal vaccine.

3. To evaluate absolute vaccine efficacy of aQIV versus non-influenza comparator when administered as a single dose to prevent first occurrence culture-confirmed influenza, due to strains antigenically unmatched to the strains selected for the seasonal influenza vaccine.
4. To evaluate the absolute efficacy of aQIV versus non-influenza comparator when administered as a single dose to prevent first occurrence RT-PCR-confirmed influenza due to any strain of influenza regardless of antigenic match from 7 days to 180 days after vaccination or at the end of influenza season, whichever is longer (early efficacy).

Secondary Immunogenicity Objective:

5. To evaluate the immunogenicity of aQIV measured by HI titer 21 days after vaccination, against influenza strains homologous to the seasonal vaccine.

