8.1.1.2 Primary Efficacy Endpoint(s)

The primary efficacy endpoint is the time to first-occurrence of RT-PCR-confirmed influenza from 21 through 180 days after vaccination or end of the influenza season, whichever is longer.

The end of the influenza season will be defined as the end of June for Northern Hemisphere (NH) influenza season and end of December for Southern Hemisphere (SH) influenza season. For tropical countries, with no typical NH or SH influenza season, the season is defined by the use of the strains in the vaccine formulation (i.e. strains as recommended for the NH or the SH influenza season) and the timing of vaccination.

An influenza event is defined as RT-PCR- or culture-confirmed influenza infection in the setting of an influenza-like illness (ILI). The primary protocol-definition of ILI will be used to define success for the primary and key secondary efficacy endpoint.

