8.5 Sample Size and Power Considerations of Primary and Secondary Objectives

Efficacy objectives:

Sample size and power consideration for the aQIV efficacy objective is based on criteria for demonstrating efficacy in placebo controlled studies provided in CBER guidance, specifically that the study should be powered to assess the lower bound of the two-sided 95% CI of vaccine effectiveness, anticipated to be substantially above zero. This study is planned using a group sequential design. The power of Cox Regression which is planned to be used for analysis is dependent on the overall number of influenza cases, so the sample sizes on number of subjects described in this section is provided more for operational reasons. Additional information on the planning of number of subjects that may need to be enroled if it is decided to continue enrolment after interim analyses is described in [Section 8.6](#).

For the primary efficacy objective: with 1-sided alpha of 2.5% and assuming an attack rate of influenza of 3.5% among subjects enroled in the non-influenza comparator group and 1.4% among the aQIV group, i.e. 60% assumed vaccine efficacy for aQIV, 238 events (i.e. 4,860 subjects per group under the assumed ERs) are needed with 86.5% power to show the absolute efficacy of aQIV versus non-influenza comparator, in preventing first occurrence RT-PCR-confirmed influenza A and/or B, due to any strain of influenza regardless of antigenic match to the strains in aQIV, in subjects ≥ 65 years of age, using a margin of 40% for lower bound of the CI for absolute vaccine efficacy.

For the first secondary efficacy objective: with a group vaccine efficacy of 65% but expecting conservatively reduced event rates of influenza cases due to matched strains of 2.5% among subjects in the non-influenza comparator group and 0.9% among the aQIV group then 144 events has estimated power approximately 88.5% to show the absolute efficacy of aQIV versus non-influenza comparator, using a margin of 40% for lower bound of the CI.

Assuming a drop-out rate of 10%, approximately 10,692 subjects \geq 65 years, 5,346 per vaccine group will be randomized to receive either aQIV or non-influenza comparator (Boostrix®) in a 1:1 allocation ratio, stratifying by age (\geq 65 to 74 and \geq 75 years of age), study site and by low vs high risk of influenza complications (score <50 vs \geq 50).

Immunogenicity objective:

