2.2.3 Secondary Efficacy Endpoints

In addition to the primary efficacy endpoint, additional endpoints for the secondary efficacy objectives are sought, based on antigenic match of culture isolated influenza to the strains of virus contained in the seasonal vaccine.

The secondary efficacy endpoints are the time to first occurrence of culture-confirmed influenza, due to

- Influenza strains regardless of antigenic match (Secondary Efficacy Objectives 2)
- Antigenically unmatched strains of influenza virus (Secondary Efficacy Objective 3).

selected for the seasonal vaccine from Day 21 to Day 180 after vaccination or the end of the influenza season, whichever is longer.

and

- Time to first occurrence of RT-PCR-confirmed influenza due to any strain of influenza regardless of antigenic match from 7 days to 180 days after vaccination or at the end of influenza season, whichever is longer (Secondary Efficacy Objective 4).

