12.2 Secondary Objectives Analysis

Hypotheses for testing secondary objectives are formulated in the similar way as for the primary efficacy objective. If an interim analysis is performed and the trial doesn't stop, then all the subsequent secondary analysis will be tested at a reduced alpha level, i.e. what's left from the interim analysis. The confidence interval will be higher than 95% instead of 95% at the final analysis.

All secondary efficacy objectives will be evaluated based on the Efficacy FAS, but analysis for the key secondary objective will be also repeated based on Efficacy PPS. For non-key secondary objectives, if the percentage of vaccinated subject excluded from the FAS is greater than 5%, a secondary analysis based on the PPS will be performed to complement the FAS.

Similarly to the primary efficacy objectives, a Cox PH model will be used to estimate absolute vaccine efficacy VE for each secondary objective 1-4.

Criteria for evaluation : if the lower limit of the 95% two-sided confidence interval for VE estimate is greater than 40% then the secondary efficacy objectives will be demonstrated.

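### Secondary efficacy objective 4 is labelled early efficacy, but its window contains the whole primary window and adds only Days 7–20, so the planned estimate does not isolate protection before Day 21

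*Protocol*

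**What the plan says.** - **Objective 4.** Protocol 2.2 defines it as first RT-PCR-confirmed influenza of any strain "from 7 days to 180 days after vaccination or at the end of influenza season, whichever is longer (early efficacy". SAP 2.2.3 repeats the endpoint: "Time to first occurrence of RT-PCR-confirmed influenza due to any strain of influenza regardless of antigenic match from 7 days to 180 days".
- **Primary endpoint.** Protocol 8.1.1.2 has the same case definition and the same closing rule, with a later start: "RT-PCR-confirmed influenza from 21 through 180 days after vaccination or end of the influenza season, whichever is longer".
- **General window.** Protocol 2.1 says the primary and secondary efficacy objectives alike are measured on "cases of influenza occurring from 21 through 180 days after vaccination or through the end of influenza season, whichever is longer". That does not fit objective 4.
- **Model.** Under SAP 12.2, "a Cox PH model will be used to estimate absolute vaccine efficacy VE for each secondary objective 1-4", in the manner of the primary analysis. SAP 12.1 gives that model one treatment coefficient. SAP 8.2 says the study period will be split into intervals for efficacy among other things, but 8.2.3 names none.
- **Success rule.** SAP 12.2 treats the secondary efficacy objectives as demonstrated when the lower confidence limit for VE is above 40%. Protocol 8.2.2.2 and 8.4.3.2.1 say that secondary efficacy objectives other than the key one are not tested.
- **Analysis set.** The Efficacy FAS (protocol 8.3.4, SAP 7.3) requires at least 21 days of observation after vaccination.

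**The concern.** A reader will take the label to mean that objective 4 shows whether protection begins before Day 21. The only follow-up that bears on this and is not already in the primary endpoint is Days 7–20, which is 14 days. A single hazard ratio over the full window averages those 14 days with 160 or more days of primary follow-up, so the result should sit close to the primary result whatever happens early.

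The consequence comes through SAP 12.2. If the 40% rule is applied to objective 4, a vaccine that protects only from Day 21 could be reported as having demonstrated early efficacy. The primary result is not affected.

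**Working it through.** **Inputs from the documents.** Protocol 8.5 assumes attack rates of "3.5% among subjects enroled in the non-influenza comparator group and 1.4% among the aQIV group, i.e. 60% assumed vaccine efficacy for aQIV", with 4,860 evaluable subjects per group and 238 events. The season ends at "the end of June for Northern Hemisphere (NH) influenza season and end of December for Southern Hemisphere (SH) influenza season" (protocol 8.1.1.2).

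**Reproducing the plan's figures.** Cases: 4,860 × 0.035 = 170 comparator and 4,860 × 0.014 = 68 aQIV, total 238, as stated. Power by the Schoenfeld formula: √238/2 × ln(0.6/0.4) = 3.128. Subtracting 1.96 gives 87.9%, and subtracting 2.00 (one-sided 0.02275) gives 87.0%, against 86.5% stated.

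**Assumptions the documents do not supply.**
- The 238 cases (170/68, VE 60%) all fall from Day 21 onward.
- Follow-up ends at T = 180, or at T = 270 as an example of a season-end close. No vaccination dates are given.
- Risk is constant over time at first, then varied.

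**Formulas.** Days 7–20 are 14 days; the primary window is T − 20 days. With k the Day 7–20 risk relative to the later risk:
- early comparator cases c = k × 170 × 14/(T − 20)
- early aQIV cases v = c × (1 − early VE)
- primary share = 238/(238 + c + v)
- pooled HR = (68 + v)/(170 + c)
- SE of log HR = √[1/(68 + v) + 1/(170 + c)]
- chance that the lower limit exceeds 40% = Φ(ln(0.6/HR)/SE − 1.96)

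**Constant risk (k = 1).**

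| T | Early VE | c / v | Primary share | Pooled VE (approx. 95% CI) | Chance lower limit > 40% |
|---|---|---|---|---|---|
| 180 | 60% | 14.9 / 6.0 | 92.0% | 60.0% (47.6 to 69.5) | 84% |
| 180 | 0% | 14.9 / 14.9 | 88.9% | 55.2% (41.9 to 65.4) | 60% |
| 270 | 60% | 9.5 / 3.8 | 94.7% | 60.0% (47.4 to 69.6) | 83% |
| 270 | 0% | 9.5 / 9.5 | 92.6% | 56.8% (43.6 to 66.9) | 68% |

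Worked row (T = 180, early VE 0%): HR = (68 + 14.9)/(170 + 14.9) = 0.448; SE = 0.132; ln(0.6/0.448)/0.132 = 2.205; 2.205 − 1.96 = 0.245; Φ = 60%. With 2.00 in place of 1.96, to allow for one interim look, the 60% and 68% become about 58% and 66%.

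These chances use the unequal case split. On the same formula the primary analysis itself has 80.7%, so they should be compared with each other and not with 86.5%.

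**Varying early risk (T = 180, early VE 0%).**

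| k | Primary share | Pooled VE | Lower limit | Chance lower limit > 40% |
|---|---|---|---|---|
| 0.1 | 98.8% | 59.5% | 46.5% | 79% |
| 0.25 | 97.0% | 58.7% | 45.6% | 76% |
| 1.5 | 84.2% | 53.0% | 39.7% | 48% |
| 2 | 80.0% | 51.1% | 37.7% | 38% |
| 3 | 72.7% | 47.5% | 34.1% | 21% |

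With early VE 60% the share runs from 99.1% (k = 0.1) to 79.2% (k = 3). Over all these cases it is about 73–99%.

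**Days 7–20 alone (k = 1, T = 180).** If early VE is 0%, about 30 cases (15 v 15) give VE 0% with CI about −105% to 51%. If early VE is 60%, about 21 cases (15 v 6) give CI about −4% to 85%. At T = 270 there are about 13 to 19 cases. At k = 0.25 and T = 180 there are only about 5 to 7.

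**The case against.** The strongest reply is that objective 4 fully defines its own estimand and that early efficacy is only a parenthesis. Read as efficacy counted from an earlier start day, it is coherent and the planned Cox model answers it. That stands as a reading of the definition. It then describes a supportive analysis of the primary, which is a reason to drop the label.

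Second, the protocol does not test this objective, and the primary estimate will be reported beside it, so a reader could see that the two nearly coincide. This also stands. The SAP's 40% rule is nevertheless written for the secondary efficacy objectives without excepting this one. That conflict is the actual route to a wrong claim.

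Third, a separate Day 7–20 estimate would probably be inconclusive even if the vaccine worked early: at true early VE 60% the interval still includes zero. This is correct and limits what the change can deliver. A wide interval still describes the evidence on Days 7–20 more faithfully than a narrow one drawn mainly from later cases.

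A reader might also infer that the lower limit stays above 40% whatever happens early, or that a false conclusion is likely. The documents do not support either. Under constant risk the chance of clearing 40% with no early protection is about 60–68%. With the Day 180 window, the expected lower limit falls below 40% once Day 7–20 risk is 1.5 times the later risk.

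**Conclusion.** The point holds in a limited form. The planned objective 4 estimate does not isolate protection before Day 21. Under constant risk, moving from full to no protection in Days 7–20 shifts it by only about 3 to 5 percentage points (60% to 55–57%). With no early protection it lies between 47.5% and about 59% for relative early risk from 3 down to 0.25. As written, SAP 12.2 could therefore call early efficacy demonstrated when none exists.

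The 89–95% overlap is not a figure in the documents. It rests on constant risk, 238 cases from Day 21 and VE 60% from Day 21, whereas protocol 8.6 itself calls circulation seasonal and rates hard to predict. Primary-window cases still form the majority in every scenario tried (about 73–99%).

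It would be wrong to infer that the trial cannot address early protection at all. Weekly ILI surveillance and swabbing start on Day 1 (protocol 3.1, 3.5 and 5.3.3), so the Day 7–20 cases are collected. What is missing is an analysis that uses them separately. This is a modest, inexpensive improvement to a non-key secondary objective.

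**What to change.** 1. In SAP 2.2.3 and 12.2, add a descriptive Day 7–20 VE with its confidence interval. Use case counts by arm or a Cox treatment effect that changes at Day 21, and show cumulative incidence curves by arm from Day 1.
2. Base it on all randomised and vaccinated subjects still at risk at Day 7. The Efficacy FAS would condition a Day 7–20 estimate on observation continuing to Day 21.
3. Report the Day 7-to-end estimate as a supportive analysis of the primary, without the early-efficacy label.
4. State in SAP 12.2 that the 40% criterion does not apply to objective 4, in line with protocol 8.2.2.2 and 8.4.3.2.1.
5. Reconcile the Day 21 sentence in protocol 2.1 with objective 4.

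**Cost.** No new data; one model term or table plus curves, and SAP wording. Any change to the protocol's objective wording has to be classed under protocol 13.4, where changes of study objectives are amendments needing approval.

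**Downside.** The Day 7–20 estimate will be imprecise (about 13–30 cases under constant risk, fewer with pre-season vaccination) and probably inconclusive whether or not early protection exists. The text should say so in advance.

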2.3 Exploratory Objective(s)

1. To characterize the immunogenicity of aQIV using other immunological assays (such as microneutralization assay).
2. To explore potential immune correlates of protection based on HI and/or other immunological assays (such as microneutralization assay).

3. STUDY DESIGN

3.1 Overview of Study Design

The study is a phase III, stratified, randomized, observer-blind, non-influenza comparator-controlled, multicenter study to evaluate the efficacy, safety and immunogenicity of an MF59-adjuvanted quadrivalent subunit influenza vaccine compared with a non-influenza comparator vaccine in subjects ≥ 65 years of age.

The study vaccine, aQIV, contains 15 μ g of each of the four seasonal influenza strains (A/H1N1, A/H3N2, B [Yamagata and Victoria lineage]) and MF59 adjuvant. The non-influenza comparator (Boostrix[®]) vaccine will be used to provide a comparative assessment for efficacy, immunogenicity and safety.

Stratification according to age (≥ 65 to 74 and ≥ 75 years), study site and comorbidity status (at risk/not at risk) will be performed (see [Section 5.1.4, Randomization](#) and [Section 5.1.2, Screening](#)). Sample size, among other factors, depends mainly on the number of RT-PCR confirmed influenza cases observed during the influenza seasons, so the overall number of subjects to be recruited provided here may change and enrolment over multiple seasons may be required to ensure 238 PCR-confirmed influenza cases have occurred and/or based on the results of the interim analysis for efficacy and futility.

Nasopharyngeal swab samples will be analyzed in batches and the number of RT-PCR confirmed influenza cases will be reviewed on a regular basis. Once the number of RT-PCR confirmed influenza cases exceeds 119, an interim analysis for efficacy and futility with an appropriate adjustment of the type I error will be performed by an independent Data Monitoring Committee (DMC). Another interim analysis might be recommended before target 238 RT-PCR confirmed influenza cases are observed. Once the number of RT-PCR confirmed influenza cases is ≥ 238 the Sponsor will stop and unblind the trial and perform the final analysis. Stopping rules for futility and efficacy and any additional details regarding the DMC can be found in the DMC Charter.

Each subject will have two stages of study participation: Treatment Period (Day 1 to Day 22) and Follow-up Period (Day 23 to Day 366).

The study procedures consist of four (4) clinic visits, and three (3) safety phone calls. After enrolment and vaccination on Day 1, all subjects will then return to the clinic for three (3) additional clinic visits, on Days 22, 181 and 366. During the study there will also be three (3) safety phone calls on Days 15, 91 and 271. Subjects participating in the solicited safety subset will receive an additional call on day 3 reminding them to complete their diary card.

Additionally, all subjects will receive weekly phone calls or messages to assess for primary protocol-defined ILI symptoms during the active ILI surveillance period, defined as from Day 1 through Day 181 or until the end of the influenza season, whichever is longer. The purpose of the ILI surveillance phone calls/message is to trigger a clinic or home visit to collect a nasopharyngeal swab. Subjects will also be asked for the duration of the trial (up to Day 366) to contact the site at the onset of ILI symptoms to schedule a clinic visit for NP swab collection.

After an initial screening, subjects will be vaccinated with a single dose of aQIV or non-influenza comparator on Day 1. Subjects will be observed for at least 30 minutes post-vaccination on Day 1 for any immediate reactions. A subset of randomly selected subjects from both treatment groups will be chosen to participate in a solicited safety subset. Subjects participating in the solicited safety subset will receive a Subject Diary along with instructions and training to ensure proper completion and assessment of reactogenicity. Each subject in the solicited safety subset will be instructed to document in their Subject Diary solicited local and systemic adverse events that may occur post-vaccination from Day 1 through Day 7. Subjects in the solicited safety subset will be asked to return their completed Subject Diary at their Day 22 clinic visit.

For all subjects, any unsolicited adverse event and concomitant medication use, after vaccination from Day 1 to Day 22 will be collected at the Day 15 safety phone call and during the Day 22 clinic visit. Information collected at these visits will be documented in the subject's source records and captured in the Electronic Case Report Form (eCRF). All subjects will also receive an ILI booklet on Day 1, and will be instructed to measure their body temperature using the thermometer provided starting from onset day of primary protocol defined ILI to the day they come into the clinic for their NP swab collection. Subjects will be asked to return the ILI booklet at the time of their NP clinic visit.

During the remaining follow-up phase of the study, safety data including adverse events leading to withdrawal, AESI, NOCD and SAE and concomitant medication use related to these events will be captured via safety phone calls or clinic visits throughout the remainder of the trial (up to Day 366).

Subjects experiencing an ILI will have one (1) additional clinic visit and one (1) additional safety call: (1) a clinic or home visit to collect a nasopharyngeal swab as soon as possible within 3, but up to 6, days after the first day of onset of primary protocol-defined ILI symptoms, and (2) a safety follow-up call 30 days after ILI onset to determine if subsequent medically-attended adverse events occurred and if any concomitant medication associated with these adverse events were used. The use of anti-viral medications will be permitted after NP swab has been obtained and will be documented as concomitant medications. Nasopharyngeal swabs will be processed for viral culture

and RT-PCR confirmation. Culture positive samples will undergo antigenic characterization.

One season in which at least 2800 subjects are anticipated to be enrolled will be selected for the collection of immunogenicity samples. Samples from approximately 2800 subjects participating in the selected season will be collected at Day 1 (baseline) and Day 22 (visit 3). In order to maintain the study blind equal numbers of subjects from both treatment groups will be asked to provide blood specimens (see [Section 3.5, Collection of Clinical Specimens](#)). After all of the blood specimens have been obtained a subset of samples from those collected will be randomly selected on a 4:1 ratio (1,362 aQIV; 340 Boostrix) for the purpose of completing the analysis of the immunogenicity objectives. Serum samples from subjects with RT-PCR confirmed influenza, along with a subset of subjects who did not have RT-PCR confirmed influenza, may be tested to estimate the correlate of protection. The serologic component of the correlate of protection will be measured using either a validated haemagglutination inhibition (HI) and/or other immunological assays (such as microneutralization).

Study Case Definition of Influenza-Like-Illness

Two definitions of ILI will be used. Primary protocol-defined ILI will be used to trigger nasopharyngeal swab retrieval ([Section 3.5, Collection of Clinical Specimens](#)) and completion of the ILI booklet ([Section 3.4.2, Tools Used for Data Collection](#)). The respiratory symptoms in both definitions are considered a new onset or exacerbation of a pre-existing condition.

- *Primary protocol-defined ILI:* At least one of the following respiratory symptoms: sore throat, cough, sputum production, wheezing, or difficulty breathing; concurrently with at least one of the following systemic symptoms: temperature of $> 37.2^{\circ}\text{C}/99^{\circ}\text{F}$, chills, tiredness, headache, or myalgia.
- *Modified CDC ILI definition:* Fever (temperature of $> 37.2^{\circ}\text{C}/99^{\circ}\text{F}$) with cough or sore throat.

The ILI onset day is defined as the first day that the subject meets the primary protocol-defined ILI.

The ILI end date is defined as the date the last symptom resolves.

A new ILI episode will only be taken into account after resolution of the previous one, as judged by the investigator (suggested interval between two ILI episodes is 14 symptom-free days).

